2. RATIONALE, OBJECTIVES, AND BENEFIT - RISK ASSESSMENT

2.1 RATIONALE FOR PERFORMING THE TRIAL

Angiogenesis is the formation of new blood vessels from pre-existing vasculature and is a key process in tumor growth. The Ang2/Tie2 and the VEGF/VEGFR2 pathways have been identified as key pathways mediating tumor angiogenesis (R13-0448). Multiple studies have described increased VEGF levels in a variety of human cancers and the VEGF expression levels have been correlated with poor survival (R15-1720). The VEGF neutralizing monoclonal antibody bevacizumab has demonstrated anti-tumor activity in clinical trials and is currently approved for several indications and settings, mainly in combination with standard chemotherapy regimens (R15-1222).

Studies in mice have shown that Ang2, a ligand of the Tie2 receptor, controls vascular remodeling by enabling the functions of other angiogenic factors, such as VEGF (R12-3593). Ang2 is primarily expressed by endothelial cells, strongly induced by hypoxia and other angiogenic factors and has been demonstrated to regulate tumor vessel plasticity, allowing vessels to respond to VEGF and FGF2 (R12-3834).

The inhibition of Ang2 is currently being tested in Phase II/III trials of the peptibody Trebananib in ovarian cancer. In a randomized Phase III trial in patient with recurrent ovarian cancer Trebananib was tested in combination with paclitaxel compared to chemotherapy alone and demonstrated improvement in PFS (7.2 month vs 5.4 months, HR 0.66 95% CI 0.57-0.77, p< 0.0001) (R14-5440).

Unfortunately, the anti-tumor activity of VEGF blockers and Ang2 blockers is not durable and only a limited number of patients benefit from such therapies. New therapeutic strategies are needed to improve outcome of metastatic/advanced cancer patients.

Pre-clinical data demonstrate that improved efficacy can be achieved by combined inhibition of VEGF and Ang2 (R14-5320, R14-5323). This observation was confirmed by internal data (c02353882).

This supports testing BI 836880 in human with the objective to improve patients' outcome. First step for this clinical development is to define the safety profile of BI 836880 and the recommended dose for further development.

2.2 TRIAL OBJECTIVES

Primary objective:

• To determine the maximum tolerated dose (MTD) of BI 836880 given as weekly intravenous infusion and to determine recommended phase II dose.

Secondary objective:

• To provide preliminary safety data

Page 19 of 99

13 Mar 2019

Trial Protocol Proprietary confidential information © 2019 Boehringer Ingelheim International GmbH or one or more of its affiliated companies

2.3 BENEFIT-RISK ASSESSMENT

BI 836880 has not been tested in human so far. In the 13-week toxicology study in cynomolgus monkeys, BI 836880 was well tolerated up to the highest tested dose of 60 mg/kg.

Anti-VEGF or anti-VEGF-R antibodies have been largely tested in clinic with a well-defined safety profile. Most commonly reported adverse events with such compounds are fatigue, hypertension, proteinuria, diarrhea and bleeding (epistaxis). Severe adverse events include gastrointestinal perforations, tumor haemorrhage and arterial thromboembolism (R14-3588, R14-3261).

There is less clinical experience with anti-Ang2 compared to VEGF pathway blockade clinical experience. The most advanced anti-angiopoietin compound (Trebananib) in development is in Phase III in combination with chemotherapy (R14-5440). Other anti-Ang2 compounds are currently in early stage of clinical development (R15-1645, R15-1646, R15-1648). From this clinical experience the most commonly reported side effects are fatigue and gastro-intestinal symptoms (diarrhea, nausea and vomiting). No bleeding or thromboembolic events were reported with this class of compound. Of note, almost all tested anti-Ang2 molecules failed to define a MTD (R15-1646, R15-1648).

Limited clinical experience of dual blockade is available. Recently, Phase I data of the bispecific human anti-Ang2/anti VEGF-A antibody (RG7221) were reported. MTD was not reached with only one dose limiting toxicity (DLT) reported (fatal pulmonary hemorrhage). Hypertension was the most common observed adverse event (R15-1644).

Based on this clinical available data it is expected that blockade of both targets will result in similar side effects as anti-VEGF and anti-Ang2 blockade. Based on the phase I trial results of RG7221 no increase in side effect severity is anticipated with BI 836880. It is anticipated that the safety profile of BI 836880 will most likely include fatigue, hypertension, proteinuria, gastro-intestinal side effects and bleeding.

Previous clinical experience with nanobodies in different disease showed acceptable safety profile with no specific side effect related to this technology (R13-2303).

Because additional adverse event not previously observed with anti-VEGF and anti-Ang2 may also occur in humans, and taking in consideration BI 836880 toxicology study results, patients will be closely monitored for the development of adverse events that may results from BI 836880 administration, with a special attention to renal function and immunogenic side effect.

Page 20 of 99

Proprietary confidential information © 2019 Boehringer Ingelheim International GmbH or one or more of its affiliated companies

Although rare, a potential for drug-induced liver injury is under constant surveillance by sponsors and regulators. Therefore, this trial requires timely detection, evaluation, and follow-up of laboratory alterations of selected liver laboratory parameters to ensure patients' safety (see also Section 5.3.6.1)

Because of the early stage of development of BI 836880 no reproduction toxicity or genotoxicity studies were performed. Because of advanced stage of the disease of phase I studies populations, women of childbearing potential can be included in this study. To minimize the risk of unintentional exposure of an embryo or foetus to the investigational drug, women of childbearing potential must agree to the requirements for pregnancy testing and contraceptive methods described in this protocol.

A Data Safety Board (DSB) will be appointed to periodically review and monitor data from the trial (refer to Section 3.1.1).

Overall, BI 836880 is expected to have an acceptable safety profile and an adequate risk/benefit in patients with locally advanced or metastatic solid tumor who are either refractory after standard therapy for the disease or for which standard therapy is not reliably effective.

3. DESCRIPTION OF DESIGN AND TRIAL POPULATION

3.1 OVERALL TRIAL DESIGN AND PLAN

This is a Phase I, multi-centre, non-randomized, uncontrolled, open-label, dose escalating study of BI 836880 administered intravenously. The eligible patient population will be patients with advanced solid tumors. Dose escalation will be guided by a Bayesian logistic regression model with over dose control (details refer to Section 7), restricted to a maximum 200% dose increment for the first dose escalation and maximum of 100% dose increment for dose \geq 120 mg. At any time during the trial, it will not be permitted to escalate to a dose which does not fulfil the escalation with overdose control (EWOC) criterion (refer to Section 7).

For any dose-escalation cohort, at least 2 patients will be required. At first dose level, first patient will be treated and observed for at least 2 weeks before allowing the second patient to receive BI 836880 infusion. For subsequent dose levels within dose escalation, each patient in a given cohort (dose level) will be observed for a minimum of 48 hours after first BI 836880 application before allowing treatment for subsequent patient in the same cohort.

In case only 2 patients are evaluable and neither has experienced a DLT within the first course, then dose-escalation can occur based on these 2 patients. However, should one of these 2 patients experience a DLT in the first course, a third patient will be enrolled at the same dose level. After all patients in a cohort have either experienced a DLT or have been observed for at least one course (3 weeks) without a DLT, the Bayesian model will be updated with the newly accumulated data. The overdose risk will then be calculated for each dose, and escalation will be permitted to all doses which fulfil the EWOC criterion and the dose escalation scheme according to Section 4.1.3. Decision on further recruitment (dose escalation, de-escalation or cohort expansion) will be made by a Data Safety Board (DSB) based on the collected safety data as well as other data (e.g. PK/PD data) when available.

If DLTs are observed in the first two consecutive patients of a previously untested dose level, subsequent enrolment to that cohort will be stopped. The Bayesian logistic regression model will be re-run to confirm that the dose-level still fulfils the EWOC criterion. Decision will be made whether the next patients will be enrolled on the same dose level, or if they will be enrolled to a lower dose level.

c03124055-06

Proprietary confidential information © 2019 Boehringer Ingelheim International GmbH or one or more of its affiliated companies

[figure not shown]

Figure 3.1: 1Study design

All patients eligible after the screening will be administrated with BI 836880 weekly infusion. In case the patient shows a stable disease or even a response, the study treatment will continue until one of the withdrawal criteria listed in Section 3.3.4 is met.

An estimated of about 25-30 patients will be necessary to establish MTD and confirm RP2D. Confirmation of the RP2D will be made based on all available safety, PK and Pharmacodynamics (PD) data at all treatment courses and all dose levels.

All patients will have regular evaluations for assessment of safety parameters as detailed in the Flow Chart.

An End of trial (EOT) evaluation is to be completed when a patient permanently discontinues the study drug, for any reason listed in Section 3.3.4.

A Follow-up evaluation will be completed 42 days after permanent discontinuation of the study drug. Refer to the Flow Chart for details. This visit will be defined as the last visit in the on-study period for the trial.

For adverse event collection, please refer to Section 5.3.6.

Page 23 of 99

Proprietary confidential information © 2019 Boehringer Ingelheim International GmbH or one or more of its affiliated companies

After the interim data base lock, the study is considered completed when the last patient in the study has discontinued the study treatment and completed the EoR visit (see Section 6.2.3.5).

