4.1.4 Drug assignment and administration of doses for each patient

The study drug will be prepared according to "Instruction for Pharmacists" which will be filed in ISF. Upon notification of an entered patient in the study, the pharmacy will prepare the study drug in the assigned dosage for administration to the patient.

BI 836880 will be given as weekly intra-venous infusion by authorised site staff in a specialized unit where emergency care can be provided (e.g. intensive care unit available, medical personal trained in advanced live support) according to "Instruction for Pharmacists". The expected infusion time is 90 min. in case no relevant infusion reactions are observed, this may be shortened to about 30 min but should not be prolonged to more than 6 hours even in case of technical issues. Appropriate drugs and medical equipment to treat anaphylactic reactions must be immediately available and study personal must be trained to recognize and treat anaphylaxis.

If symptoms of an infusion-related reaction CTCAE grade ≥ 2 occur (that are not qualifying as DLT according to Section 5.3), the infusion should be temporarily stopped. Upon recovery, infusion should be resumed at 50% of the rate at which the reaction occurred. Depending on the time of occurrence and the severity of the reaction, the investigator may consider administrating additional supportive medication, e.g. corticosteroids for reintroduction. Infusion rate and premedication for further treatment courses should be adapted according to Investigator decision, but adaptation of application scheme need to be agreed with sponsor.

BI 836880 will be administrated intravenously starting on course1 day1. In the event of delay or interruption of treatment due to adverse event, BI 836880 infusion should be skipped; and the next scheduled BI 836880 infusion should be administrated upon recovery to CTCAE Grade 1.

Premedication: No premedication will be required for BI 836880 IV infusion.

If a patient experienced sign of infusion reaction at any BI 836880 treatment, a premedication will be **considered** for all subsequent treatment infusions (dosage and schedule according to investigator's decision) comparable to the following scheme:

- Acetaminophen/paracetamol 650 mg-1000 mg p.o., or equivalent
- Antihistamine p.o. or i.v., equivalent to Diphenhyldramine 50 mg i.v.
- Glucocorticoid i.v., equivalent to prednisolone 100 mg

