5.3 ASSESSMENT OF SAFETY

Dose Limiting Toxicity (DLT)

The following drug-related adverse events will qualify as Dose-Limiting Toxicities:

- CTCAE grade \geq 3 non haematological toxicity except:
 - ➤ Vomiting or diarrhea responding to supporting treatment
 - Fatigue lasting for less than 4 days
 - Transcient Grade 3 infusion reaction (i.e. if infusion- related reaction can be controlled by appropriate medication according to investigator's decision and next infusion will not be delayed for more than two weeks).
 - Any laboratory abnormality, which is considered not clinically relevant by the investigator or resolves spontaneously or can be resolved with appropriate treatment. Clinically relevant abnormalities have to be documented as AE (see Section 5.3.6)
- CTCAE grade 4 neutropenia >7 days or complicated by infection (in case of neutropenia grade 4, close observation of patient is necessary.
- CTCAE grade >3 febrile neutropenia
- CTCAE grade = 4 thrombocytopenia
- CTCAE grade > 3 thrombocytopenia with bleeding
- CTCAE grade > 3 proteinuria (urinary protein > 3.5 g/day)
- Hypertension: increase of diastolic blood pressure (BP) by 15 mmHg confirmed by second measurement or ambulatory blood pressure measurement (when indicated; e.g. white coat effect) which cannot be controlled by hypertensive medication and requires a dose reduction of BI 836880 for further treatment course.
- All related AE leading to an interruption of BI 836880 for more than 14 days until recovery to baseline.

The MTD may be considered reached if the probability that the true DLT rate is in target interval (16%-33%) is sufficiently large (for details see Section 7). The DSB may recommend stopping the dose finding phase after the criterion for MTD is fulfilled.

If the next dose level is recommended by the statistical model, however, the efficacy is considered sufficient at current dose level, the DSB may decide to include additional number of patients at this dose level and declare this dose as RP2D and no further dose escalation will happen.

Based on the overall data after all patients on proposed RP2D have been treated for at least 1 course, the DSB will make a final determination of RP2D.

Page 39 of 99

13 Mar 2019

Trial Protocol Proprietary confidential information © 2019 Boehringer Ingelheim International GmbH or one or more of its affiliated companies

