7. STATISTICAL METHODS AND DETERMINATION OF SAMPLE SIZE

7.1 STATISTICAL DESIGN – MODEL

This is phase I, open-label, dose-escalating trial to determine the MTD and RP2D for BI 836880 in patients with solid tumors. MTD is defined as the highest dose with less than 25% risk of the true DLT probability being above 33%, and may be considered reached if the probability that the true DLT rate is in target interval (16%-33%) is sufficiently large. Dose escalation and determination of MTD will be guided by a Bayesian 2-parameter logistic regression model with overdose control (R13-4803, R13-4806). These designs have been shown to be superior regarding the precision of MTD determination compared to 3+3 designs and have been particularly endorsed by the FDA (R13-4881).

The model is formulated as follows:

 $logit(p(d)) = log(\alpha) + \beta * log(d/d*),$

where logit(p) = log(p/(1-p)).

p(d) represents the probability of having a DLT in the first course at dose d, $d^* = 1250$ mg is the reference dose, allowing for the interpretation of α as the odds of a DLT at dose d^* , and $\theta = (\log(\alpha), \log(\beta))$ with α , $\beta > 0$ is the parameter vector of the model.

Since a Bayesian approach is applied, a prior distribution $\pi(\theta)$ for the unknown parameter vector θ needs to be specified. This prior distribution will be specified as a mixture of three multivariate normal distributions, i.e.

$$\pi(\theta) = \phi_1 \pi_1(\theta) + \phi_2 \pi_2(\theta) + \phi_3 \pi_3(\theta)$$

with

 $\phi_i,\,i=1,\,2,\,3$ the prior mixture weights $(\phi_1+\,\phi_2+\,\phi_3=1)$

and

$$\pi_i(\theta) = MVN(\mu_i, \Sigma_i)$$

the multivariate normal distribution of the i-th component with mean vector μ_i and covariance matrix Σ_i , with

$$\Sigma_{i} = \begin{pmatrix} \sigma_{i,11}^{2} & \sigma_{i,11}\sigma_{i,22}\rho_{i} \\ \sigma_{i,11}\sigma_{i,22}\rho_{i} & \sigma_{i,22}^{2} \end{pmatrix}$$

Mixture prior distributions have the advantage that they allow for specification of different logistic dose-toxicity curves, therefore making the prior more robust.

Prior derivation

For the current study, no relevant information in the form of human data was available, since no study in a comparable population has been conducted. Therefore, the three mixture components were established as follows:

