5. ENDPOINT(S)

5.1 PRIMARY ENDPOINT(S)

The objective of this study is to determine the safety and tolerability of BI 836880. The primary endpoint is the determination of the maximum tolerated dose (MTD) of BI 836880 based on the number of patients with dose-limiting toxicities (DLTs) during the first treatment cycle. The DLT is defined in section 5.3 of the CTP.

The MTD is defined as the highest dose with less than 25% risk of the true DLT probability being above 33%, and may be considered reached if the probability that the true DLT rate is in target interval (16%-33%) is sufficiently large during the MTD evaluation period.

The MTD evaluation period is defined as the time within 3 weeks after first administration of study treatment.

Patients who have not completed one cycle of treatment will be replaced. Patients who were replaced during the MTD evaluation period will not be considered for MTD determination. Those patients that have completed the MTD evaluation period without having been replaced will be referred to as patients evaluable for MTD.

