6.2 IMPORTANT PROTOCOL VIOLATIONS

A protocol violation (PV) is important if it affects the rights or safety of the study patients, or if it can potentially influence the primary outcome measurements in a non-negligible way. Patients with important PVs that could potentially impact the evaluation of the primary endpoint(s) will be excluded.

A list of important PVs is given in Table 6.2: 1 below. Important PVs will be reviewed at Medical Quality Review Meetings (MQRMs) conducted periodically during the trial. A list of protocol deviations will be discussed at the blinded report planning meetings (BRPMs).

If the data show other important PVs, this table will be supplemented accordingly at MQRMs or BRPMs or through team review of the manual PV log. The decision whether a patient will be excluded from the analysis will be made at the final BRPM prior to DBL.

Table 6.2: 1 Important protocol violations

| Category / | | Description | Requirements | Excluded | |
|------------|------|--------------------------------------|---|----------|--|
| Cod | le | | | from | |
| A | | Entrance criteria not met | | | |
| | A1 | Inclusion criteria not met | | | |
| | A1.1 | Requirements on age or birth control | Inclusion criteria 1 or 8 | None | |
| | | not met | | | |
| | A1.2 | Disease severity not met | Inclusion criteria 2 | None | |
| | A1.3 | Adequate health condition not met | Inclusion criteria 3, 4, 6, or 7 | None | |
| | A2 | Exclusion criteria not met | | | |
| | A2.1 | Hypersensitivity to the trial drug | Exclusion criteria 1 | None | |
| | A2.2 | Previous anti-cancer therapy | Exclusion criteria 2 | None | |
| | | washout period not met | | | |
| | A2.3 | Clinically relevant concomitant or | Exclusion criteria 3, 4, 5, 6, 7, 8, 9, 10, or 11 | None | |
| | | history of disease, pre-existing | | | |
| | | conditions | | | |

Table 6.2: 1 Important protocol violations (cont.)

| Cate | egory / | Description | Requirements | Excluded from |
|---|------------------------------|---|---|---------------|
| A | | Entrance criteria not met | | HOIII |
| | A2.4 | Under judicial protection and legally institutionalized | Exclusion criteria 12 | None |
| A2.5 Requirement of adherence to protocol not met | | 1 * | Exclusion criteria 13 | None |
| | | | Exclusion criteria 14 | None |
| В | | Informed consent | | |
| | | | Informed consent date missing | All |
| | B2 Informed consent too late | | Informed consent date was after screening visit date | None |

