| С | | Trial medication and randomisation | | |
| | C1 | Incorrect trial medication taken | To be determined on a case by case basis. Listing will be created and decision will be made at MQRM / BRPM, e.g., incorrect dose taken, dose in course 1 not following dose escalation scheme, overdose, use of expired medication etc. | None |
| | С3 | Non-compliance | Study drug not taken according to protocol. To be determined on a case by case basis. Listing will be created and decision will be made at MQRM / BRPM e.g., outside of dosing schedule window, unreasonable drug administration time, etc. | None |
| | C5 | Re-treatment criteria not met | Re-treatment criteria was not met according to CTP section 4.1.4 | None |
| D | | Concomitant medication | | |
| | D2 | Prohibited medication use | Refer to CTP section 4.2.2.1. | None |
| Z | | Other | | |
| | Z3 | Missing critical safety information in cycle 1 | Essential safety information for the evaluation of DLT is missing | None |

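### Evaluability for the MTD is stated in conflicting ways, with no minimum course-1 exposure or DLT data, and one patient can decide whether the current dose meets the overdose limit

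*Protocol*

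**What the plan says.** **Time basis.** In Protocol 7.1 the modelled quantity p(d) "represents the probability of having a DLT in the first course at dose d". Protocol 3.1 updates the model when every patient in the cohort has had a DLT or "have been observed for at least one course (3 weeks) without a DLT, the Bayesian model will be updated". Protocol 6.2.2 defines a course as 21 days. SAP 5.1 says "The MTD evaluation period is defined as the time within 3 weeks after first administration of study treatment". None of these names a number of infusions.

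**Skipping.** If an adverse event interrupts treatment, Protocol 4.1.4 says the "BI 836880 infusion should be skipped; and the next scheduled BI 836880 infusion should be administrated upon recovery to CTCAE Grade 1". An interruption is itself a DLT only under this item of Protocol 5.3: "All related AE leading to an interruption of BI 836880 for more than 14 days until recovery to baseline".

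**Who is evaluable.** Protocol 3.3.4.1 replaces patients who did not complete the first course, unless the reason was drug-related toxicity. SAP 5.1 replaces anyone who has not completed one cycle. SAP 7.4 excludes patients who did not complete the three-week period for a reason other than DLT.

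**Violations.** SAP 6.2 states: "Patients with important PVs that could potentially impact the evaluation of the primary endpoint(s) will be excluded". In Table 6.2:1, code Z3 reads "Essential safety information for the evaluation of DLT is missing", and its exclusion column says None. So do C1 (incorrect medication, including a wrong course-1 dose) and C3 (drug not taken per protocol). Exclusions are decided at the final report planning meeting before database lock.

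**The concern.** A DLT-free patient is evidence that a dose is tolerated only if the patient received the regimen and was assessed for DLTs. The plan secures neither. A patient who missed an infusion because of toxicity short of a DLT can be scored as a full success at the assigned dose. A patient with essential DLT information missing is not removed by the table that should remove them. Cohorts are two or three patients, so one patient weighs heavily. Any exclusion settled at the final meeting also comes after every escalation decision has been taken.

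The protocol's own figures suggest exposure matters: accumulation in monkeys was about 2-fold on repeated dosing (Section 1.2), and the target trough is expected after 7 infusions at 120 mg but after 2 at 360 mg (Section 4.1.3).

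**Working it through.** **1. The three rules side by side.**

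| Patient | Protocol 3.3.4.1 | SAP 5.1 | SAP 7.4 |
|---|---|---|---|
| Leaves course 1 early, reason not drug-related | replaced | replaced | excluded |
| Leaves course 1 early, drug-related toxicity short of a DLT | kept | replaced | excluded |
| Skips an infusion, on study to day 21, no DLT | depends on undefined 'completed' | depends on undefined 'completed' | not excluded |
| Stops in course 1 with a DLT | kept | replaced if read literally | kept |

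Only the first row agrees. In the third row, a skip directed by Section 4.1.4 follows the protocol, so code C3 need not catch it either.

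**2. The 14-day item.** Suppose days 8 and 15 are both skipped and dosing resumes on day 22. From the missed infusion: 22 − 8 = 14 days, not more than 14. From the last infusion received: 22 − 1 = 21 days, more than 14. The start of the count is not stated.

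**3. Model.** Inputs are from Protocol 7.1 and Table 7.1:1.

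- logit p(d) = log α + β·log(d/1250)
- Prior on (log α, log β): weight 0.90, mean (0.740, 0.798), SD (2, 1); weight 0.05, mean (0.846, −0.123), SD (2, 1); weight 0.05, mean (−2.731, 0.193), SD (5, 0.01); all correlations 0
- Likelihood: product over doses of p(d)^r·(1 − p(d))^(n − r), for r DLTs in n patients
- P(OD) = posterior probability that p(d) ≥ 0.33; limit 0.25

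The posterior was integrated on a 1601 × 1601 grid for each prior component.

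**4. Reproducing Table 10.6:1.**

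| Scenario, dose | Printed P(OD) | Recomputed |
|---|---|---|
| 1, at 120 mg | 0.062 | 0.064 |
| 2, at 40 mg | 0.318 | 0.325 |
| 4, at 120 mg | 0.231 | 0.237 |
| 5, at 120 mg | 0.623 | 0.630 |
| 5, at 40 mg | 0.237 | 0.230 |
| 7, at 480 mg | 0.229 | 0.227 |

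The largest gap is 0.007.

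**5. Weight of one DLT-free patient.** The cohort has 1 DLT, and lower cohorts are DLT-free (0/2 at 40 mg, 0/2 at 120 mg, 0/3 at 240 mg, as far as they apply). Entries are P(OD) at the current dose, by the weight given to the third patient. The fractional weights are illustrative.

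| Dose | Full (1/3) | Weight 2/3 | Weight 1/3 | Excluded (1/2) |
|---|---|---|---|---|
| 120 mg | 0.237 | 0.269 | 0.304 | 0.344 |
| 240 mg | 0.210 | 0.237 | 0.267 | 0.301 |
| 480 mg | 0.227 | 0.256 | 0.288 | 0.323 |

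Every dose passes at full weight and fails on exclusion. If the third patient's missing data hid a DLT (2/3), P(OD) would be 0.630 at 120 mg and 0.588 at 480 mg.

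**6. Does it affect escalation?**

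- With 1 DLT in 3, the next listed dose fails anyway after 120 mg: 150 mg gives 0.316. The next dose in the simulated grid fails after 240 mg: 480 mg gives 0.583. After 480 mg, 720 mg gives 0.562.
- With no DLTs, dropping one patient leaves the next dose under the limit: 40 to 120 mg, 0.064 to 0.094; 120 to 240 mg, 0.065 to 0.090; 240 to 480 mg (0/3 to 0/2), 0.097 to 0.118.

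**The case against.** Four stronger readings are tempting, and the documents do not support them.

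- *Every patient with one or two infusions enters as DLT-free.* Not so. Protocol 3.3.4.1 replaces those who leave for reasons unrelated to the drug, SAP 5.1 and 7.4 remove more, and SAP 6.3 limits the dose-finding set to evaluable patients. The gap is the patient who skips but stays, and the row on which protocol and SAP disagree.
- *Missing DLT data are scored as no DLT.* No passage says so. SAP 6.2 contradicts itself, and Protocol 5.3.3 counts unproven recovery from grade 4 neutropenia as a DLT.
- *The gap lets the dose rise past the overdose limit.* Step 6 shows no such case. In a two-patient cohort, losing one patient would leave only the minimum of two evaluable patients unmet.
- *Two skipped infusions are never a DLT.* This depends on where the 14-day count starts.

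There are also safeguards. The DSB weighs all safety and PK/PD data. Protocol 3.1.1 leaves the minimum data for escalation to the DSB charter, which is not available here. With 1 DLT in 2, Section 3.1 already calls for a third patient. These points narrow the concern. They do not settle which of three evaluability rules governs, and under the present text the skipping patient fills the third place, so no replacement is sought.

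**Conclusion.** The concern holds in this limited form. The primary analysis rests on an evaluability rule that is stated inconsistently and has no exposure or data requirement, and the SAP contradicts itself on missing DLT information. One patient of doubtful evaluability can decide whether the current dose meets the limit when 1 of 3 has a DLT: P(OD) rises by about 0.09 to 0.11 and crosses 0.25 at 120, 240 and 480 mg. At two-thirds weight it still crosses at 120 and 480 mg, but not at 240 mg. The decisions in Table 10.6:1 scenarios 2, 3, 6 and 8 do not change.

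This rests on the stated prior, DLT-free lower cohorts, and the doubtful patient being in the current cohort. The documents give no frequency of skipped infusions, so how often this would arise is unknown, and the charter may already contain part of the remedy.

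**What to change.** 1. **SAP Table 6.2:1.** For patients without a DLT, change None to the primary MTD analysis for Z3, and for C1 and C3 when course 1 is affected. Apply this before each model update, not only at the final meeting.
2. **One definition of evaluable for MTD**, used in Protocol 3.1 and 3.3.4.1 and SAP 5.1 and 7.4. Patients with a DLT always count. A patient without a DLT counts only with a sponsor-fixed minimum course-1 exposure and complete DLT assessments; otherwise the patient is replaced, subject to item 3. The per-visit compliance in SAP 7.3 can supply the exposure measure, provided an unattended visit counts as zero; at present only attended visits enter.
3. **Infusions missed through drug-related toxicity short of a DLT.** Reconcile Protocol 3.3.4.1 with SAP 5.1 and 7.4. Simple replacement would discard patients who carry toxicity information. Show the DSB the model with the patient counted as DLT-free and as a DLT.
4. **Interruption item in Protocol 5.3.** State the day from which the 14 days are counted, and align the DSB charter with items 1 to 3.

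The cost is a few sentences in each document and an occasional replacement patient.
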